7. DAWBA – SDO

1. DAWBA bands

For each disorder rated the DAWBA¹⁰ produces bands indicating the percentage of children with these scores who (from the ONS datasets) would meet DSM/ICD criteria for that particular disorder:

Level 0: <0.1% of children in this band have the disorder

Level 1: ~0.5% of children in this band have the disorder

Level 2: ~3% of children in this band have the disorder

Level 3: ~15% of children in this band have the disorder

Level 4: ~50% of children in this band have the disorder

Level 5: >70% of children in this band have the disorder

- ICD-10 disorders will be grouped into four categories (any anxiety or OCD; conduct or oppositional; hyperkinesis; depression). In multiple disorder categories the disorder with the highest Likelihood level will be used.
- Data will be presented in two Venn diagrams, for PACT and TAU, using the cutpoint of >50% for disorder present. Group differences in rates assessed using ordinal logistic regression.
- 2. Strength and Difficulty Questionnaire scores

SDQ¹¹ Peer problems and prosocial scores to be analysed by ordinal regression for group difference, covarying for imbalance baseline covariates.

References

- (1) [name], [name], [name], [name], [name], [name], [name], [name], Hudry K, [name], Barrett B, Temple K, Macdonald W, [name]; PACT Consortium. (2010) Parent-mediated communication-focused treatment in children with autism (PACT): a randomised controlled trial. Lancet 19, 2152-60. doi: 10.1016/S0140-6736(10)60587-9.
- (2) Gotham K, [name], Lord C. Standardizing ADOS Scores for a Measure of Severity in Autism Spectrum Disorders. J Autism Dev Disorder 2009;39:693-705.
- (4) [name], [name], Emsley R, [name] M. Brief report: mediation of treatment effect in a communication intervention for pre-school children with autism. J Autism Dev Disorder 2011;42:447-54

APPENDIX 1: Major post application revisions incorporated in this version

Outcomes:

The principal outcome, the ADOS CSS, remains unchanged.

The language outcome remains unchanged.

The FLQ is demoted from primary to secondary in the light of concern about no available publication for the measure.

Measures from the DCMA measuring mother-child interaction are promoted in the light of other work on the mechanism analysis of the PACT trial, that highlighted these measures in understanding treatment mechanism (Pickles et al 2014). Of the available codes, Child Initiations was considered the best proximal outcome, given the results of this mechanism analysis. Conversational turns and mutual shared attention were included as child secondary outcomes. Parent Synchrony was included as a secondary informative as to treatment mechanism. Measures to be constructed as in the original trial.

With the FLQ demoted, but an ongoing concern to represent the parent perspective, potential generalization of effects into the school domain and growing awareness of comorbidities the parent and teacher Vineland ABC, the parent reported SCQ and RBQ, and SDQ and DAWBA are added as additional secondary outcomes.

APPENDIX 2: Subsequent revisions occurring post data inspection

During analysis:

- (1) Two secondary outcomes were dropped: i) Mutual Shared Attention from the DCMA interaction coding that had been suggested for descriptive reporting but on later testing in independent middle childhood samples had been found to be unreliable and age-inappropriate; ii) family life score from the FLQ questionnaire for which published validation had not yet become available;
- (2) For the longitudinal models the Area-Under-the-Curve estimates were added as a means of summarizing treatment effect over the course of the study and multiple imputation and GEE/robust standard error estimation was used as an additional check as the robustness of the findings to model misspecification and missing data;
- (3) A proposed Venn-diagram spanning five categories of co-occurring disorders from the DAWBA was dropped as being too disaggregated to be interpretable;
- (4) Bootstrap standard errors were used for the confidence intervals of all effect estimates as their properties were likely to be superior to those based on standard asymptotics for many of the statistics presented;
- (5) The inclusion of dummy variables for centre effects.

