- a. The enhanced parental synchronous communication with their child produced in the PACT intervention arm will (as predicted by theory and previous evidence) differentially enhance later child language and communication abilities compared to the non-PACT treated arm.
- b. The enhanced parent / child dyadic communication achieved in the intervention arm will have differential secondary impact on downstream autism symptoms, both in social communication and repetitive and stereotyped behaviour domains.
- c. The impact of PACT intervention in self-report family functioning seen at trial endpoint, will be sustained at follow-up and have downstream effect on child development, predicted by theory, in terms of improved social adaptation and decreased co-morbid psychopathology.
- d. Test of potential long-term moderators of intervention outcomes in development. These include baseline variables identified in the initial PACT trial, including SES, autism severity, initial IQ, and traits of the 'broader autism phenotype' in parents undertaking the intervention.

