9. MEASURES

9.1 Primary outcome measures

The primary outcomes measures are:

Autism Symptom Outcomes

- Autism Diagnostic Observation Schedule (ADOS) symptom severity

Language Outcomes - standardised scores of receptive and expressive language

- Clinical Evaluation of Language Fundamentals Fourth Edition UK
- Receptive/ Expressive One Word Picture Vocabulary Tests Fourth Edition

Family functioning and parental wellbeing

- -Family Life Questionnaire
- Parent Wellbeing Questionnaire

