10.4 Analysis plan

Primary analysis of the data will take place within the University of Manchester, King's College London or the University of Newcastle, by [name] (Trial Statistician) or [name] (Chief Investigator). Other team members will have access to the data and undertake analyses as appropriate. Any arrangements for other researchers in the general field to have access to the primary data will be negotiated separately and COREC informed.

Stage 1: Preliminary analyses will approach the follow-up data using the traditional Intention-To-Treat method, covarying for baseline values of measures corresponding to outcomes, and for measures of parental educational qualifications and SES baseline factors, identified previously as unbalanced across treatment groups. The primary outcomes will be: language and communication outcomes (CELF, ROWPVT); family functioning (FLQ) and the ADOS, for which we shall make use of the cross-module standardized severity scores (Gotham et al., 2009). Missing data will be multiply imputed, using only imputations of the baseline variables where the analysis model is maximum likelihood (and thus able to exploit properties of ML for ignorable non-response). Analysis will use appropriate generalised linear models, where possible, using models for repeated measures growth curves fitted to baseline, outcome and follow-up. These will characterise not only an overall effect but also the extent to which later effects are consistent with a magnification or attenuation of the early effects observed in the original trial. Having repeated measures will increase our potential power but, for some analyses, we will need to account for multiple testing (the previous PACT findings essentially forming an interim analysis).

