16. REFERENCES

1) [name]. [name], T. [name], H. et al (2010). Parent-Mediated Communication-Focused Treatment for preschool children with Autism (PACT); a randomised controlled trial. *The Lancet*, 375(9732), 2152-2160.

PACT 7-11 SUMMARY OF PROTOCOL AMENDMENTS

The following changes have been made to the protocol from v.1 to v3.

Version Number	Date	Section	Amendment
v.2	05.09.13	General Information, 12. Study Monitoring and 13. Dissemination	These sections have been updated to reflect the following changes: new website address; addition of new Research Associate; change to Trial Steering Committee members.
		7. Timeline	The timeline has been changed to allow more time for start-up tasks and staff training (from April 2013 to June 2013).
		8.3. Assessment Procedures and 9.3 Measures	The SF36v.2 Health Survey has been replaced by the Parent Wellbeing Questionnaire. These sections have been changed to reflect this change. Details of the Parent wellbeing Questionnaire have been added.
		8.3. Assessment Procedures and 9.3 Measures	The Manchester Playground Observation Measure (MIPO) has been added to the protocol and new information about this measure has been added in these sections.
v. 3	22.11.13	8.3 Assessment Procedures and 9.3 Description of Measures	The Autism Diagnostic Interview-Revised (ADI-R) is no longer part of the assessment battery and has been replaced by the Social Communication Questionnaire (SCQ) and Repetitive Behaviour Questionnaire (RBQ). Therefore the ADI-R information has been deleted and details of the SCQ and RBQ have been added in these sections.

PACT 7-11 ANALYSIS PLAN FOR THE PRIMARY FOLLOW-UP PAPER

Authors: [name], [name], [name], [name], [name], [name], [name], [name], [name], [name], [name], [name], [name], [name], [name], [name], [name].

Agreed 21/1/15 prior to inspection of follow-up data by treatment group

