Appendix 1: Major post application revisions incorporated in this version

Appendix 2: Subsequent revisions occurring post data inspection

Document Revised for publication 29/1/16

STUDY DESIGN AND TRIAL ENDPOINT ANALYSIS

As described in Green et al. (2010).

FOLLOW-UP ANALYSIS

Overall strategy

Intention-to-Treat analysis of original trial/randomization design.

Primary outcomes: ADOS, DCMA, Language composite Secondary outcomes: VABS, RBQ, FLQ, DAWBA, SDQ, SCQ

Analysis goal: to use all the data to obtain good estimates of outcome where possible using growth curve approaches to yield a group difference at the median follow-up age (elaborated in PART A below) or as a simple follow-up difference or latent regression (elaborated in PART B below). No imputation of baseline data required.

Description

Follow-up rates to be described and balance in baseline covariates among those followed up to be described. CONSORT type diagram in on-line supplement.

Table 1 with Baseline and Follow-up mean/proportion/median and SD/range by treatment group for gender, age-at-recruitment, age-at-follow-up, numbers by centre.

Table 2 Follow-up mean/proportion/median and SD/range by treatment group for primary and secondary measures.

Treatment differences to be summarized in a tree-plot like effect size diagram.

PACT 7-11 Office, University of Manchester, [name]

PACT 7-11 Combined Protocol and Analysis Plans with Changes 1/2/16 Page 24

Part A

Growth Curve Analysis model: For **repeated measures** (i.e. those already measured in PACT) treatment group comparisons at the mean age at follow-up based on a piecewise growth curve model with separate correlated pieces over PACT and PACT7-11. Baseline variables for which groups are imbalanced will be included as fixed-effect covariates with interactions of group and time to allow different effects during PACT and PACT7-11. Group differences will be estimated at the median follow-up age.

Primary Outcomes

1. ADOS-2 overall Comparative Severity Score (CSS)². Then report Social Affect and Restricted and Repetitive Behavior Comparative Severity Scores³ descriptively. The numbers completing each ADOS Module will be reported.

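### The Family Life Questionnaire, kept with a specified analysis despite having no publication, was dropped after data inspection for essentially that same known reason

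*Combined protocol and SAP*

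**What the plan says.** - Protocol 9.1 lists the FLQ as primary, in a family functioning and parental wellbeing domain. Section 10.4 agrees: "The primary outcomes will be: language and communication outcomes (CELF, ROWPVT); family functioning (FLQ) and the ADOS".
- Section 9.1 lists a second instrument in that domain, the "Parent Wellbeing Questionnaire". Section 10.4 does not name it.
- The analysis plan for the primary follow-up paper carries the line "Agreed 21/1/15 prior to inspection of follow-up data by treatment group". Its Overall strategy gives "Primary outcomes: ADOS, DCMA, Language composite" and "Secondary outcomes: VABS, RBQ, FLQ, DAWBA, SDQ, SCQ".
- Appendix 1 explains the change of rank: "The FLQ is demoted from primary to secondary in the light of concern about no available publication for the measure".
- Part A, item 4 nevertheless specifies an analysis of the FLQ total, using the model for the parent Vineland, and remarks there that the measure had no published reference.
- Appendix 2, item (1), drops two secondary outcomes during analysis. One is Mutual Shared Attention. The other is the "family life score from the FLQ questionnaire for which published validation had not yet become available".
- Three objectives bear on this domain: question 2c in section 5.1; question 3c in section 5.1, which predicts "The impact of PACT intervention in self-report family functioning seen at trial endpoint, will be sustained at follow-up"; and secondary objective 3 in section 5.2.

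**The concern.** A pre-specified outcome should leave the analysis after inspection only for a reason that is new and independent of the result. Here the reason was already on record. It had been dealt with once by demotion, and the plan then committed to an estimate with the limitation in view. Using it again after inspection removes a planned estimate at a time when its value could have been known.

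At stake is the only remaining planned outcome for parent-reported family functioning. Section 5.2 says that PACT parents reported relatively better family wellbeing at the end of the trial. Loss of that benefit by middle childhood would be an important finding, and so would its persistence.

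**Working it through.** No arithmetic settles this point. The documents give no FLQ effect, standard deviation or power, so no numerical bias can be computed. The check is to follow each measure through the documents.

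**Status of the two family instruments**

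| Place | FLQ | Parent Wellbeing Questionnaire |
|---|---|---|
| Protocol 9.1 | primary | primary |
| Protocol 10.4 | primary | not named |
| Analysis plan (21/1/15) | secondary, model in Part A, item 4 | absent |
| Appendix 1 | demotion explained | not mentioned |
| Appendix 2 (after inspection) | dropped | not mentioned |

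Outcomes for parent-reported family functioning or parental wellbeing: 2 in protocol 9.1, 1 in the analysis plan, 0 after Appendix 2.

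**Was the reason new?** Three statements can be set side by side. Appendix 1 gives lack of a publication as the ground for demotion. Part A, item 4 notes the lack of a reference while specifying the model. Appendix 2 gives the continuing lack of published validation as the ground for removal. The first two belong to the plan agreed before inspection by group, and the third reports that nothing had changed. Neither the Overall strategy nor item 4 makes the analysis conditional on publication.

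**Comparison within the same item.** Mutual Shared Attention was planned for descriptive reporting only. It was dropped on later evidence from independent samples that its coding was unreliable and unsuited to the age group. That is a new fact from outside the trial. No counterpart is given for the FLQ.

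**Timing.** The plan is dated 21/1/15 and the revised document 29/1/16. That is 365 + 8 = 373 days. The removal itself is not dated, and Appendix 2 does not say whether FLQ results had been seen by group.

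**What else left the plan.** Sections 9.1 and 9.2 list 11 outcome instruments: ADOS, CELF, one-word tests, FLQ, Parent Wellbeing Questionnaire, parent Vineland, teacher Vineland, MIPO, CA-SUS, Time Diary and DAWBA. Four are absent from the analysis plan: the Parent Wellbeing Questionnaire, CA-SUS, Time Diary and MIPO. The FLQ makes 4 + 1 = 5 after Appendix 2. Only the FLQ left after inspection.

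**What remains for the objectives.** Parent and teacher Vineland, DAWBA, SDQ and parent synchrony stay. The measures that Appendix 1 adds for the parent perspective describe the child. Parent synchrony is observed interaction, not family functioning or wellbeing.

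**The case against.** The strongest reply is that the removal is disclosed, with its timing and reason, and that the wording fits a team waiting for a validation paper that did not arrive. Declining to headline an unvalidated scale is a respectable scientific choice. Nothing in the documents shows that the FLQ result by group was known or that it influenced the decision. All of that stands. It does not supply the missing estimate, and the plan set no such waiting condition.

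Several stronger readings are tempting, and the documents do not support them.

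- *Family outcomes were removed selectively.* Mutual Shared Attention was dropped in the same item, and the MIPO, a playground measure, is also absent. The family-side absences other than the FLQ are already present in a plan dated before inspection by group.
- *The Parent Wellbeing Questionnaire may have been left out because of its result.* Its omission predates inspection by group on the documents' own dating, so this is an unexplained change of status. Its primary rank is itself unclear, because 9.1 and 10.4 disagree. Nor could it show whether gains at PACT endpoint lasted: section 9.3.5 says that the FLQ was used in PACT and says no such thing of this questionnaire.
- *The family objectives go untested.* Secondary objective 3 also covers child adaptation and child mental health, which are still analysed.
- *No treatment comparison was ever reported.* The plan covers the primary follow-up paper only, and other papers cannot be seen from here.

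**Conclusion.** The concern holds for the FLQ. A secondary outcome with a specified model was removed after data inspection on a limitation already recorded and accepted in the plan, so a reader cannot exclude result-dependent omission. Its size is one pre-specified estimate, and with it the last outcome in the primary-paper plan for parent-reported family functioning or parental wellbeing. That leaves part of questions 2c and 3c and of secondary objective 3 without a test in that plan. The question of sustained family benefit rests on the FLQ alone.

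This takes the dates and headings in the document at face value. It is a finding about what a reader can rule out, and it does not claim that results drove the decision. The Parent Wellbeing Questionnaire is a lesser documentation gap.

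**What to change.** 1. Report the FLQ total treatment difference with its interval, from the model in Part A, item 4, in the effect-size diagram or the supplement, labelled 'no published validation'.
2. State in Appendix 2 whether the FLQ result by group was known when the measure was dropped.
3. Reconcile the status of the Parent Wellbeing Questionnaire across 9.1, 10.4 and the analysis plan. Either report its two component scores (the General Health Questionnaire-12 and the Warwick and Edinburgh scale) under the Part B regression, or say where they will be reported.

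The cost is at most 1 + 2 = 3 further estimates and a few explanatory sentences, assuming that the data were collected as section 8.3 planned. The FLQ model is the one already fitted to the parent Vineland. The downside is that an unvalidated measure appears in the results, which the label addresses.
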